8.2. Statistical Analyses

One-way ANOVA will be used to compare the natural log transformed AUC_{last} , AUC_{inf} (if data permit) and C_{max} for PF-07321332 between Cohort 2 with moderate hepatic impairment (Test) and Cohort 1 with normal hepatic function (Reference). Estimates of the adjusted mean differences (Test-Reference) and corresponding 90% CIs will be obtained from the model. The adjusted mean differences and 90% CIs for the differences will be exponentiated to provide estimates of the ratio of the adjusted geometric means (Test/Reference) and 90% CIs for the ratios.

Box and whisker plots for individual participant parameters (AUC_{inf} , AUC_{last} and C_{max}) will be constructed by cohort and overlaid with geometric means.

Residuals from the models will be examined for normality and the presence of outliers via visual inspection of plots of residuals vs predicted values and normal probability plots of residuals but these will not be included in the clinical study report. If there are major deviations from normality or outliers then the effect of these on the conclusions will be investigated through alternative transformations and/or analyses excluding outliers. Justification for any alternative to the planned analysis will be given in the report of the study.

The following PK parameters will be summarized by analyte and hepatic function group as applicable:

Table 3. PK Parameters to be Summarized Descriptively by Group	
Parameter	Summary Statistics
CCI, AUC _{last} , AUC _{inf} , C _{max} , CCI	N, arithmetic mean, median, cv%, standard deviation, minimum, maximum, geometric mean and geometric cv%.
CCI	

Supporting data from the estimation of t_{1/2} and AUC_{inf} will be listed by group: terminal phase rate constant (k_{el}); goodness of fit statistic from the log-linear regression (r²); the percent of AUC_{inf} based on extrapolation (AUC_{extrap%}); and the first, last, and number of time points used in the estimation of k_{el}. This data may be included in the clinical study report.

Presentations for PF-07321332 CCI (where applicable) concentrations will include:

- A listing of all concentrations sorted by hepatic function group (present in heading), subject id and nominal time postdose. The concentration listing will also include the actual times. Deviations from the nominal time will be given in a separate listing.
- A summary of concentrations by hepatic function group and nominal time postdose, where the set of statistics will include n, mean, median, standard deviation, coefficient of variation (cv), minimum, maximum and the number of concentrations above the lower limit of quantification.
- Median concentrations time plots (on both linear and semi-log scales) against nominal time postdose by hepatic function group (all hepatic function groups on the same plot per scale, based on the summary of concentrations by hepatic function group and time postdose).

- Mean concentrations time plots (on both linear and semi-log scales) against nominal time postdose by hepatic function group (all hepatic function groups on the same plot per scale, based on the summary of concentrations by hepatic function group and time postdose).
- Individual concentration time plots by hepatic function group (on both linear and semi-log scales) against actual time postdose (there will be separate spaghetti plots for each hepatic function group per scale).
- CCI [REDACTED]
[REDACTED].

For summary statistics, median and mean plots by sampling time, the nominal PK sampling time will be used, for individual subject plots by time, the actual PK sampling time will be used.

8.3. Safety Analysis

A set of summary tables split by hepatic function group will be produced to evaluate any potential risk associated with the safety and toleration of administering PF-07321332.

8.3.1. Treatment and Disposition of Subjects

Subject evaluation groups will show end of study subject disposition and will show which subjects were analyzed for pharmacokinetics, as well as for safety (adverse events and laboratory data). Frequency counts will be supplied for subject discontinuation(s) by hepatic function group.

Data will be reported in accordance with the sponsor reporting standards.

8.3.2. Demographic and Clinical Examination Data

A break down of demographic data will be provided for age, race, weight, body mass index, and height. Each will be summarized by sex at birth and ‘All Subjects’ in accordance with the sponsor reporting standards by cohort.

8.3.3. Discontinuation(s)

Subject discontinuations, temporary discontinuations or dose reductions due to adverse events will be detailed and summarized by hepatic function group.

Data will be reported in accordance with the sponsor reporting standards.

8.3.4. Adverse Events

Adverse events will be reported in accordance with the sponsor reporting standards by hepatic function group.

8.3.5. Laboratory Data

The baseline measurement is the last planned predose measurement.

For each planned timepoint, baseline values and change from baseline values within each hepatic function group will be summarized with descriptive statistics (using sponsor default standards).

These data will be listed in accordance with the sponsor reporting standards.

8.3.6. Vital Signs Data

Supine blood pressure and pulse rate will be measured at the time points as mentioned in the schedule of activities in the protocol.

The baseline measurement is the last planned predose measurement.

Vital Signs data will be databased and available upon request.

8.3.7. ECG Data

The baseline measurement is the last planned predose measurement.

ECG data will be databased and available upon request.

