## 3. OBJECTIVES AND ENDPOINTS

Objectives	Endpoints
Primary:	Primary:

To compare the PK of PF-07321332, following a single oral dose administration of PF-07321332 pharmacokinetically boosted with ritonavir in adult participants with moderate hepatic impairment and age and body weight-matched participants without hepatic impairment.

	

Plasma PF-07321332 PK parameters: <math>C_{max}</math>, <math>AUC_{last}</math>, <math>AUC_{inf}</math>(if data permit)

Secondary:	Secondary:

To evaluate the safety and tolerability of PF-07321332 and ritonavir, following a single oral dose administration of PF-07321332 pharmacokinetically boosted with ritonavir, in participants with moderate hepatic impairment and in healthy participants with normal hepatic function.

	

Incidence of TEAEs, abnormal ECGs, vital signs, and laboratory values

CC1 	

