### **9.3.1. Other Safety Analyses**

All safety analyses will be performed on the safety population.

AEs, and safety laboratory data will be reviewed and summarized on an ongoing basis during the study to evaluate the safety of participants. Any clinical laboratory, ECG, BP, and pulse rate abnormalities of potential clinical concern will be described. Safety data will be presented in tabular and/or graphical format and summarized descriptively, where appropriate.

Medical history and physical examination and neurological examination information, as applicable, collected during the course of the study will be considered source data and will not be required to be reported, unless otherwise noted. However, any untoward findings identified on physical and/or neurological examinations conducted during the active collection period will be captured as AEs, if those findings meet the definition of an AE. Data collected at screening that are used for inclusion/exclusion criteria, such as laboratory data, ECGs, and vital signs, will be considered source data, and will not be required to be reported, unless otherwise noted. Demographic data collected at screening will be reported.

CCI

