6.2. Safety Endpoints

Any events occurring following start of treatment (of PF-07321332) or increasing in severity will be counted as treatment emergent.

Events that occur in a non-treatment period (for example, Follow-up) will be counted as treatment emergent and attributed to the previous treatment taken.

The following data are considered in standard safety summaries (see protocol for collection days and list of parameters):

- *adverse events*,
- *laboratory data*.

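### Two of the four parts of the secondary safety endpoint, abnormal ECGs and vital signs, have no table or listing planned in the SAP

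*SAP*

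**What the plan says.** Protocol section 3, and the synopsis, give the secondary endpoint as "Incidence of TEAEs, abnormal ECGs, vital signs, and laboratory values". Protocol 9.3.1 adds: "Any clinical laboratory, ECG, BP, and pulse rate abnormalities of potential clinical concern will be described". It also says that safety data will be tabulated or graphed where appropriate. It does not say by cohort.

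The SAP is narrower. In section 6.2, the sentence beginning "The following data are considered in standard safety summaries" is followed by two items, adverse events and laboratory data. Section 8.3.4 reports adverse events by hepatic function group. Section 8.3.5 summarises laboratory baseline and change from baseline by group, and lists the data. For vital signs, section 8.3.6 ends with "Vital Signs data will be databased and available upon request". For ECG, section 8.3.7 ends with "ECG data will be databased and available upon request". Both of these sections define a baseline ("The baseline measurement is the last planned predose measurement"), but neither uses it in any planned display.

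**The concern.** An endpoint named in the protocol should have a planned result. If the SAP is followed as written, the report will contain no count of participants with abnormal ECGs or abnormal vital signs in either cohort, although the endpoint names both. It will not necessarily contain a count for abnormal laboratory values either.

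Timing matters too. The study is open-label and both documents allow the sponsor to review data during the study. If no criteria for an abnormal reading are fixed beforehand, any later count would rest on criteria chosen after data could have been seen.

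**Working it through.** The plan gives no figure to reproduce. The check sets the endpoint against the planned outputs and then sizes what is missing.

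**1. Endpoint components against SAP outputs**

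| Component | Where in SAP | Any table or listing? | Incidence of abnormal findings stated? |
|---|---|---|---|
| TEAEs | 6.2, 8.3.4 | Yes, by group | Not spelled out; assumed to come with the sponsor's AE standards |
| Laboratory values | 6.2, 8.3.5 | Yes, by-group summary and listing | No |
| Vital signs | 8.3.6 | No | No |
| ECG | 8.3.7 | No | No |

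The two columns are different tests. On the test of any output, 4 − 2 = 2 components are missing. On the stricter test of a stated incidence, laboratory values fall short as well, making 3 of 4.

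**2. Whether another section supplies the output**

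- The opening of SAP 8.3 promises by-group safety tables in general but names none for ECG or vital signs.
- SAP 8.3.1 again describes the safety data as adverse events and laboratory data.
- SAP 8.3.9, on other safety data, reads None.
- Sections 8.3.1 to 8.3.5 and 8.3.8 refer to sponsor standards. Sections 8.3.6 and 8.3.7 do not, so those standards cannot be read in as the missing plan.

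**3. Whether the AE tables give the same result**

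Under Protocol Appendix 3, an abnormal ECG or vital sign becomes an adverse event when the investigator considers it clinically significant. Abnormalities associated with the underlying disease are excluded unless they are more severe than expected. An AE count is therefore a filtered subset of abnormal readings. The disease exclusion bears mainly on Cohort 2, the Test group.

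**4. Size of what is missing**

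Inputs: 16 participants, 8 per cohort (Protocol Table 1). The Schedule of Activities marks ECG and vital signs alike at Screening, Day 1 and Day 3, with nothing on Day −1 or Day 2. For each type:

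- Screening: 16 × 1 = 16
- Day 1, before PF-07321332: 16 × 1 = 16
- Day 3, after PF-07321332: 16 × 1 = 16, or 8 per cohort

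These are minimum counts. Footnotes h and i mention further specified times without naming them, and an early-termination visit adds a reading. With 8 per cohort, one participant is 1/8 = 12.5%, so any table is descriptive.

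**5. Which reading is the baseline**

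SAP 8.3.6 and 8.3.7 do not name the dose that predose refers to, and ritonavir starts on Day −1. However, footnotes h and i and Protocol 4.1 place the predose ECG and vital signs on Day 1. SAP 6.2 also starts treatment emergence at PF-07321332. Protocol 9.3.1 points the same way: "Data collected at screening that are used for inclusion/exclusion criteria, such as laboratory data, ECGs, and vital signs, will be considered source data", which need not be reported. SAP 8.3.11 does not list screening data. The baseline is therefore the Day 1 reading, taken after the first ritonavir dose and before PF-07321332.

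**The case against.** The best defence is that little is lost. Protocol 9.3.1 still commits the sponsor to describing ECG, blood pressure and pulse-rate abnormalities, and silence in the SAP does not revoke that. Clinically significant findings will appear in the by-group AE reporting. The data are held and retrievable, and the scheduled information after PF-07321332 is about one reading of each type per participant. All of this stands, and it limits the weight of the point. It does not supply the incidence that the endpoint names.

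Four stronger readings are tempting, and the documents do not support them:

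- **A breach of procedure.** Protocol section 9 lets the SAP modify the outlined analyses and requires an amendment only for major changes to the primary endpoints or their analysis. The weakness is that the SAP does not present or explain the omission as a change.
- **An undefined baseline, possibly Screening.** The passages in step 5 of the working point to Day 1. A clarifying phrase would help, but this is not a second defect.
- **The other two components are fully covered.** Laboratory values have output, but not an explicit incidence of abnormal values.
- **Appendix 7 can be used whole as the ECG criteria.** Some of its categories depend on duration, such as bradycardia lasting minutes, or Wenckebach block or ventricular rhythms beyond 30 seconds. Protocol 8.2.3 specifies an ECG with a 10-second rhythm strip, and the scheduled assessment is single, so it cannot establish those.

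**Conclusion.** The mismatch is real. Two of the four components of the secondary endpoint have no planned table or listing, and a third has output but no stated incidence. It should be fixed before analysis, at the lower end of importance: the effect is confined to descriptive safety reporting, and the primary PK comparison is untouched.

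The conclusion assumes that the sponsor's AE standards yield TEAE incidence by group, and that the sponsor has no separate output plan outside these documents that adds ECG and vital-sign tables. If such a plan exists, citing it in SAP 8.3.6 and 8.3.7 would largely close the point.

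**What to change.** Add ECG and vital signs to SAP 6.2. In 8.3.6 and 8.3.7, replace the closing sentence with a listing and n (%) of participants per cohort meeting criteria fixed before analysis:

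- **ECG:** the Appendix 7 criteria that a single tracing can show, for example QTcF above 480 msec or an increase of at least 60 msec, new PR above 280 msec, and new bundle branch block.
- **Blood pressure and pulse:** criteria written into the SAP, since none for reporting are visible in the documents.
- **Laboratory values:** add to 8.3.5 the n (%) of participants with abnormal values.

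The alternative is to change the secondary endpoint and Protocol 9.3.1 to match the SAP, and record the change.

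Two minor clarifications can go in at the same time. State that baseline is the Day 1 reading before PF-07321332. Reconcile the supine blood pressure in SAP 8.3.6 with the seated measurement in the Schedule of Activities, its footnote i, and Protocol 8.2.2.

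The cost is a few small descriptive tables and two listings from data already collected, partly overlapping with AE reporting, plus agreement on the blood pressure and pulse criteria. The alternative costs a recorded change to the protocol.

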8.3.8. COVID-19 Data

These data will be listed in accordance with the sponsor reporting standards.

8.3.9. Other Safety Data

None.

8.3.10. Concomitant Treatments

All concomitant medication(s) as well as non-drug treatment(s) will be provided in the listings.

8.3.11. Screening and Other Special Purpose Data

If such data will be brought in-house, then it will not be listed.

9. REFERENCES

None.

10. APPENDICES

Appendix 1. SAS CODE FOR ANALYSES

An example of the PROC GLM code is provided below:

```
proc mixed data = tab.pk covtest alpha=0.1;
  class group;
  model l&var = group / S covb alpha=0.1 CL DDFM=KR;
  repeated/type=un subject=subjid group=group R;
  lsmeans group;
  estimate 'Moderate vs Normal'      group 1 -1;
  ods output lsmeans = lsmeans&var;
  ods output solutionf = solution&var;
run;
```

/* Letter assignments for group within the estimate statement above are as follows;

A = *Moderate* (Test);
B = *Normal* (Reference); */;
